^a The planned dose levels (including the dose levels allowed to increase the dose in the same cohort) may be changed following review of data from Parts A and B, and the emerging data from Part C. However, for each of the cohorts the doses will not exceed the doses previously tested in Part A and Part B. In addition, the increase from one dose level to the next dose level within the same cohort or between cohorts will not be more than 3-fold.

^b Doses have now been selected as per protocol based on data from all patients of Cohort C1 who have completed the Main Treatment Period (n=12).

Part C may commence after the first 3 cohorts of Part B have been completed, providing there is sufficient appropriate data available (safety and tolerability, PK, and PD) to enable determination of dose levels.

The following table provides an overview of the doses (μ g) planned to be adminstered in Part C

^b Part C may commence after completion of the first 3 cohorts of Part B.

The follow-up visit will take place on Day 37 (±2 days) only for patients not entering the extension period. The Sponsor is prolonging the treatment period of each of the Part C cohorts (patients with HP) with an open label extension of 2 months. Eligible patients will therefore remain treated with AZP-3601 and will not perform the follow-up visit. This extension period will allow collection of efficacy and safety data over a longer-term period (3 months) and treatment protocol is adressed in the current protocol amendment.

Before proceeding to the second cohort, the SRC will review the data of the first cohort. Review will be performed on safety and tolerability data, available PD data (with at least serum and urinary calcium, serum phosphate, and number of patients achieving reduction/elimination in calcium and active vitamin D supplements), and available PK data. In addition, the safety data of each of the cohorts will be reviewed on a regular basis during the treatment period.

Although this is an ascending dose study, a lower dose may be administered in the second cohort based on the safety, tolerability, or available PD and plasma PK results of the first cohort. Also, the same dose may be tested or an intermediate dose may be tested to gain more information on safety, tolerability, PD, and/or PK.

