There will be an interval of at least 7 days between the last dose in the first cohort and the first dose in the second cohort. Subjects included in the first cohort cannot participate in the second cohort.

Part C, Extension Phase

Patients completing the 4 weeks Main Treatment Period of Part C, will be offered to enter a 2-months open label treatment extension phase. For patients willing to enter the extension phase, an ICF should be signed on Day 28 at the latest.

Patients will have to complete study assessments up to Day 28, as described in Table 3 and from Day 29 onwards, as described in Table 4.

Patients who will not participate to the Extension phase will have to complete study assessments as described in Table 3.

The overall study schematic for the Extension Phase of Part C, is presented hereafter (for more details, please refer to the Schedule of Assessments – Part C, Extension Phase in Table 4

The 2 month open label treatment extension phase will start immediately following Day 28 visit of the Main treatment period. Patients will receive AZP-3601 for 56 days (2 months) as daily sc injections from Day 29 onwards (with rotation of injection sites each day of administration).

The goal is to optimize AZP-3601 dosing across a dose range while doses of oral calcium and active vitamin D are as low as safely possible and albumin-corrected serum calcium is maintained within the target range of 7.8 to 9.0 mg/dL (1.95 to 2.25 mmol/L) together with an optimal control of the symptoms of hypoparathyroidism.

For patients who are taking minimal or no supplemental calcium (≤500 mg/day) and no vitamin D on Day 28, the AZP-3601 dose from the previous 14 days of treatment (Part C, Main Treatment Period) can be maintained and adjusted when needed during the Extension Phase.

For patients who are still taking active vitamin D and/or more than 500 mg/day of oral calcium on Day 28, a progressive reduction of supplements will be carried out while increasing the dose of AZP-3601.

On Day 29 onwards, patients will continue on the same dose of AZP-3601 as on Day 28, then individual titration of AZP-3601 may start as early as Day 30 and patients may have their dose of AZP-3601 adjusted at any time during the Extension Phase.

Patients may have their AZP-3601 dose increased, as previously defined, with the goal of achieving or maintaining albumin-corrected serum calcium in the target range of 7.8 to 9.0 mg/dL (1.95 to 2.25 mmol/L).

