8.1.3 Descriptive Statistics

Unless otherwise indicated, continuous variables will be summarized with the following descriptive statistics: number of observations (n), (arithmetic) mean, SD, minimum (min) value, median, and maximum (max) value. For PK data, geometric mean and geometric CV will be presented in addition.

• Geometric mean = exp(m), where m is the arithmetic mean of the log-transformed data.

EDSREP 009 T 01 G Page 13 of 53

Version Date: 26-Aug-2022

Geometric CV (%): sqrt(exp(s*s)-1)*100, where s*s is the variance of the log-transformed data.

Categorical data will be summarized with frequencies and percentages. Percentages by categories will be based on the number of subjects exposed within a treatment.

For categorical data, the categories will be presented in the tables exactly as they appear in the electronic case report form (eCRF) / Database. No data manipulation will be done for presentation purposes.

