9.1 Safety Set

All subjects who have received at least 1 dose of AZP-3601 or placebo.

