17.1.2 Deaths and Serious Adverse Events

A listing of deaths and other serious adverse events (SAE) will be provided by subject.

1	7.	1.3	Inje	ction	Site	Rea	ctions
---	----	-----	------	-------	------	-----	--------

,									,				
Α	summary	table	with	the	number	and	percentage	of	subjects	reporting	injection	site	reactions
са	tegorized b	ov seve	eritv e	valu	ation, will	be p	resented by I				/col	hort (for Part C

and overall at each scheduled assessment timepoint for each study part.

Injection site reactions as collected on the CRF will be listed per subject.

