17.1.4 Laboratory Data

Clinical laboratory data will be presented using standard units from the SDTM Controlled Terminology.

Descriptive statistics summarizing continuous laboratory results of clinical chemistry, hematology and coagulation (absolute observed and derived changes from baseline) for each study part by //cohort (for Part C) and scheduled time will be presented.

Frequency table summarizing categorical laboratory results of urinalysis for each study part by //cohort (for Part C) and scheduled time will be presented, if appropriate.

All laboratory data will be listed by subject.

A separate listing of clinically significant abnormal values will also be provided.

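### By-timepoint safety percentages are divided by all exposed patients, so at Day 37 every patient who entered the extension counts as reaction-free without having been assessed

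*SAP*

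**What the plan says.** The general rule on categorical data in SAP 8.1.3 reads: "Percentages by categories will be based on the number of subjects exposed within a treatment". Exposure needs one dose and no assessment; the Safety Set (SAP 9.1) is "All subjects who have received at least 1 dose of AZP-3601 or placebo".

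Two categorical safety tables are built by timepoint. SAP 17.1.3 gives counts and percentages of injection-site reactions by severity, per cohort "and overall at each scheduled assessment timepoint for each study part". SAP 17.1.4 plans a "Frequency table summarizing categorical laboratory results of urinalysis for each study part", by cohort and scheduled time. Neither section states its own denominator. The SAP does state one elsewhere: menopause status (12.2) is expressed over female patients.

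On attendance, the Protocol synopsis (Part C) says: "The follow-up visit will take place on Day 37 (±2 days) only for patients not entering the extension period". Of the others it says: "Eligible patients will therefore remain treated with AZP-3601 and will not perform the follow-up visit". Protocol Table 3 schedules both injection-site assessment and clinical laboratory tests, including urinalysis, at that visit. Patients in the extension have their follow-up on Day 98 instead (Table 4).

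**The concern.** A reaction can be recorded only in a patient who is examined. Under the stated rule, a patient who was dosed but not examined at a timepoint adds one to the denominator and can never add to the numerator, which has the same effect as scoring that patient as free of reaction. SAP 8.1.2 does not list injection-site reactions among its imputation exceptions, so this is not a deliberate missing-data rule; it follows from the choice of denominator.

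At Day 37 the absence is planned. It affects everyone who enters the extension.

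Safety and tolerability is the primary objective (SAP 5.1), and SAP 8.4.3 plans no hypothesis tests, so the descriptive percentages are themselves the result. For continuous variables SAP 8.1.3 requires the number of observations to be shown. For categorical variables it requires only frequencies and percentages, so the text does not oblige the table to show how many patients were examined.

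**Working it through.** The documents state no reaction rate, so there is no figure to reproduce. The check is direct arithmetic.

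**Inputs**
- N, exposed: 12 per cohort, up to 2 cohorts, so 2 × 12 = 24 overall (Protocol, Part C; approximate planned sizes).
- m, assessed at the timepoint: not stated for Day 37. Completers "will be offered to enter a 2-months open label treatment extension phase", and no uptake is given. Values of m below are assumptions.
- x, patients with a reaction at the timepoint: illustrative.

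**Formulas**
- SAP percentage = 100x/N
- Assessed-patient percentage = 100x/m
- Hence SAP percentage = assessed-patient percentage × m/N
- Largest percentage the table can show = 100m/N

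**Day 37, one cohort (N = 12), one reactor (x = 1)**

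| m assessed (assumed) | SAP rule, 100/12 | Assessed patients, 100/m | Largest possible SAP figure, 100m/12 |
|---|---|---|---|
| 12 | 8.3% | 8.3% | 100% |
| 9 | 8.3% | 11.1% | 75.0% |
| 6 | 8.3% | 16.7% | 50.0% |
| 3 | 8.3% | 33.3% | 25.0% |
| 2 | 8.3% | 50.0% | 16.7% |

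The SAP figure stays the same however many patients were examined. With 3 assessed it cannot exceed 25.0%, even if all 3 react.

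**Day 37, both cohorts (N = 24), one third of those assessed reacting**
- No patient enters the extension: 8 of 24 assessed react; SAP figure 8/24 = 33.3%.
- 25% enter: 6 of 18 react; 6/24 = 25.0%.
- 50% enter: 4 of 12 react; 4/24 = 16.7%.
- 75% enter: 2 of 6 react; 2/24 = 8.3%.

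**Other main-period timepoints.** Injection sites are also assessed on Days 1, 14, 15, 16, 28 and 29 (Protocol Table 3, footnote h), when every patient still in the study is scheduled. Here m falls below N only through withdrawal or a missed visit. With 2 of 12 missing and 5 of the remaining 10 reacting, 50% becomes 5/12 = 41.7%. With none missing the figure is right.

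**Extension timepoints (Days 56, 84, 85 and 98).** The result depends on what exposed means. SAP 8.1.4 summarises by part, 8.5 treats Part C Main and Part C Extension as separate parts, 14.0 reports exposure separately for the two periods, and 17.1 summarises safety by part. Read together, exposed in an extension table means dosed in the extension, and again only withdrawals and missed visits matter. The SAP does not say so outright: 8.2.2 lists a single Part C treatment, 8.5 equates treatment with dose level, and 17.1.3 tabulates by cohort.

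**The case against.** The strongest reply is that little harm follows. Counts are printed beside percentages, every reaction is listed by patient, cohorts are small enough for a reader to reconstruct the facts, no test or decision rule uses these percentages, and the urinalysis table is produced only if appropriate. Day 37 (±2 days) is also 7 to 11 days after the last dose on Day 28, so it is not where local tolerability is mainly judged. The table shells (SAP Appendix 4) are not in the available text and may show an assessed number. All of this stands and limits the consequences. None of it changes the denominator that the SAP text states.

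A reader might infer more than the documents support:
- *That most patients are missing at Day 37.* No uptake is given. Only the absence of all entrants is certain.
- *That injection-site rates are too low throughout.* They are diluted only where someone is unassessed and at least one reaction is seen. A rate that falls over time as an artefact would need drop-out figures that the documents do not give.
- *That extension tables are diluted by patients who declined.* This needs exposed to mean the whole cohort, which is the less natural reading.
- *That early terminators have no later assessment.* The documents do not say this. Tables 3 and 4 include early-termination visits with injection-site assessment, and the Day 37 wording does not exclude these patients.
- *That the assessed-patient percentage at Day 37 is the true rate.* Attendees are those who did not enter the extension, possibly for tolerability reasons, so it may overstate the rate in the whole cohort.

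Using exposed patients for overall adverse-event incidence is appropriate and is not in question.

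**Conclusion.** The point holds, in limited form. Followed as written, SAP 8.1.3 dilutes the by-timepoint percentages in 17.1.3 and 17.1.4 by the factor assessed/exposed and never inflates them. The effect is structural at Day 37, where its size depends on an extension uptake that the documents do not state: with half of a cohort of 12 entering, the printed figure is half of the assessed-patient figure, and with 9 of 12 entering it is a quarter. Elsewhere it is incidental and modest, for example 41.7% in place of 50% with 2 of 12 missing, provided that exposed in extension tables means dosed in the extension. The conclusion also assumes that the unseen shells do not override the text. The change is worth making because the percentages serve the primary objective and the correction is small.

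**What to change.** In SAP 8.1.3, state that categorical percentages in tables by scheduled timepoint use patients with a non-missing assessment at that timepoint, displayed as n/N assessed. Define exposed per study part and cohort. In SAP 17.1.3, add one row for a reaction at any time during the part, with all patients dosed in that part as denominator; this gives a stable summary of local tolerability. Check that the Appendix 4 shells agree.

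The cost is a sentence or two of SAP text and one table row, with no new data. The drawback is that denominators will differ between timepoints, and the Day 37 percentage will rest on a small, selected group: with 2 assessed, one reactor reads as 50.0%. The n/N display makes the first visible. A footnote at Day 37 should say that only patients not entering the extension attend.

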8.1.4 Pooling

For each part, summary statistics will be calculated by treatment (and time point, if applicable).

8.1.5 Unscheduled Measurements

Unscheduled measurements will be included in the listings. Except for unscheduled measurements used for baseline, unscheduled measurements will be excluded from the descriptive statistics and statistical analysis.

8.2 Analysis Data Definitions

8.2.1 Baseline Definition

Unless otherwise stated, baseline for post-dose evaluations is defined as the last observation recorded before the first study drug administration in each study part. The last observation can be an unscheduled / repeated measurement. If a pre-treatment observation is missing then the screening value may be used.

Another exception is

the baseline definition for the main PD analysis due to the potential batch effect (see Section 16.2.1).

EDSREP 009 T 01 G Page 14 of 53

Version Date: 26-Aug-2022

8.2.2 Treatment/Subject Grouping

Label	Grouping
Study Drug	AZP-3601 and Placebo
Treatment	Port C (MAD Port in Subjects with HD)
	Part C (MAD Part in Subjects with HP) multiple sc AZP-3601
Dose Level ^a	
	Part C (MAD Part in patients with HP, Main Treatment Period) Cohort 1: 20μg qd from Day 1 to Day 28 (may be increased to 40 μg from Day 14 onwards)
	Cohort 2: 40µg qd from Day 1 to Day 28 (may be increased to 60 µg from Day 14 onwards)
	Part C (MAD in patients with HP, Extension Phase)
	During the extension phase, patients may have their AZP-3601 dose increased in increments of 10^a µg to a maximum dose of 60^a µg (Cohort 1) and of 80^a µg (Cohort 2)

^a The planned dose levels may change following review of the emerging data.

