If independence from active vitamin D and reduction of oral calcium is not achieved on Day 14 (ie, elimination of active vitamine D and reduction of oral calcium to or below 500 mg/day), the AZP-3601 dose will be increased and patients will be treated at this dose for the remaining duration of the treatment period (up to Day 28). In addition, staggered reductions of doses of oral calcium and active vitamin D supplements will therefore be performed and/or continued during the second 14 days of the Main Treatment Period according to the same principles as the first 14 days of the Main Treatment Period.

Patients achieving independence from active vitamin D and reduction of oral calcium on Day 14 will remain at the same dose level. The last remaining daily dose of oral calcium, if any, may be removed on Day 17 based on the predose albumin-corrected value of serum calcium.

Patients will undergo frequent testing for albumin-corrected serum calcium and phosphate during the initial 14-day treatment period and again following increase of the dose. In addition, there may be additional and unscheduled checks for albumin-corrected serum calcium and phosphate at the discretion of the Investigator.

At any time during the study, hypercalcemia and hypocalcemia will be managed by adjustment in active vitamin D and/or oral calcium supplementation. Adjustments will be based on laboratory values including albumin-corrected serum calcium and serum phosphate as well as on symptoms and will be performed at the Investigator's judgment. As a general guidance, adjustments should be performed when calcium values are outside the target range of 7.8 to 9.0 mg/dL, ie, 1.95 to 2.25 mmol/L.

The following treatments are administered in Part C in an open-label fashion:

- Cohort C1: multiple sc doses of 20 µg AZP-3601 (n=12) qd from Day 1 to Day 28 (dose increase of AZP-3601 to 40 µg was allowed from Day 14 onwards)
- Cohort C2^b: multiple sc doses of a fixed dose of 10^a µg AZP-3601 (n=12) qd from Day 1 to Day 28 (dose of AZP-3601 may be increased at a fixed dose of 20^a µg from Day 14 onwards)

During the extension phase, patients may have their AZP-3601 dose increased in increments of 10^a µg to a maximum dose of 60^a µg (Cohort 1) and of 80^a µg (Cohort 2)

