At any time during the study, hypercalcemia and hypocalcemia will be managed by adjustment in active vitamin D and/or oral calcium supplementation. Adjustments will be based on laboratory values including albumin-corrected serum calcium and serum phosphate as well as on symptoms and will be performed at the Investigator's judgment. As a general guidance, adjustments should be performed when calcium values are outside the target range of 7.8 to 9.0 mg/dL.

The following treatments are planned to be administered in Part C in an open-label fashion:

Cohort C1: sc doses of 20 µg AZP-3601 (n=12) qd from Day 1 to Day 28 (dose of AZP-3601 may be increased to 40 µg from Day 14 onwards)

Cohort C2: sc doses of a fixed dose up to 40^a µg AZP-3601 (n=12) qd from Day 1 to Day 28 (dose of AZP-3601 may be increased at a fixed dose up to 60 µg from Day 14 onwards)

During the extension phase, patients may have their AZP-3601 dose increased in increments of $10^a \mu g$ to a maximum dose of $60^a \mu g$ (Cohort 1) and of $80^a \mu g$ (Cohort 2).

The planned dose levels (including the dose levels allowed to increase the dose in the same cohort) may be changed following review of data from Parts A and B, and the emerging data from Part C. However, for each of the cohorts the doses will not exceed the doses previously tested in Part A and

EDSREP 009 T 01 G Page 8 of 53

Version Date: 26-Aug-2022

Part B. In addition, the increase from one dose level to the next dose level within the same cohort or between cohorts will not be more than 3-fold.

Part C may commence after the first 3 cohorts of Part B have been completed, providing there is sufficient appropriate data available (safety and tolerability, PK, and PD) to enable determination of dose levels.

The following table provides an overview of the doses (µg) planned to be adminstered in Part C

					1
D 1001 1				0.45	Ooh
Part C Cohort				C1 ^b	C2 ^b
				20 (dose 1)	fixed dose
				40 (dose 2)	up to 40
					(dose 1)
					fixed dose
					up to 60
					(dose 2)

^a Part B may commence following completion of the first 3 cohorts of Part A.

Although this is an ascending dose study, a lower dose may be administered in the second cohort based on the safety, tolerability, or available PD and plasma PK results of the first cohort. Also, the same dose may be tested or an intermediate dose may be tested to gain more information on safety, tolerability, PD, and/or PK.

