14.0 Treatment Compliance and Exposure

Exposure data of study drug, collected by CRF, will be listed by subject. In Part C, exposure data of study drug, collected by diary, will also be listed by subject. If applicable, date and time of meal intake and comments will be listed.

For Part C, exposure data of study drug will be summarized by cohort for

- Dose exposure parameters separately by main treatment period and extension phase include:
 - o Total actual dose received (µg) (Sum of all doses administered)
 - Number of doses received
 - Duration of exposure (in days) = last dose date first dose date + 1
 - Dose Intensity (μg/day) = total actual dose received / duration of exposure
 - o Relative Dose Intensity (ratio) = total actual dose received / total planned dose
- Dose increases during the main treatment period include:
 - o Doses increases at Day 15 = Yes / No (doses at Day 15 versus doses at Day 1)

EDSREP 009 T 01 G Page 19 of 53

Version Date: 26-Aug-2022

- Doses increases after Day 15 = Yes / No (doses at Day 16 or later up to Day 28 versus doses at Day 1)
- Doses increases or decreases during the extension phase (versus actual dose at Day 28) include:
 - Number of patients with one increase only (without decrease)
 - o Number of patients with at least two increases (without decrease)
 - Number of patients with one decrease only (without increase)
 - Number of patients with at least two decreases (without increase)
 - o Number of patients with both increase and decrease
 - o Number of patients with no change in dose

Study drug dispensing and returning will be listed by subject.

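### Cohort C2 dose levels conflict between SAP 8.2.2, SAP 6.0 and the protocol, and SAP 14.0 leaves the denominator of relative dose intensity undefined

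*SAP*

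**What the plan says.** - **SAP 8.2.2, Dose Level row.** Cohort 2 starts at 40 µg, and the entry continues "qd from Day 1 to Day 28 (may be increased to 60" µg from Day 14). The row's footnote reads "The planned dose levels may change following review of the emerging data". It gives no other C2 value and does not say where to find one.
- **SAP 6.0.** For C2: "sc doses of a fixed dose up to 40" µg, and from Day 14 the dose of "AZP-3601 may be increased at a fixed dose up to 60" µg. Both are ceilings, and the section also allows a lower dose in the second cohort.
- **Protocol, Part C treatments.** For C2: "multiple sc doses of a fixed dose of" 10 µg, with a possible increase to a fixed 20 µg from Day 14. Footnote b adds: "Doses have now been selected as per protocol based on data from all patients of Cohort C1" who finished the Main Treatment Period. The same 10 and 20 µg also carry footnote a, under which planned levels may still change.
- **Where the documents agree.** C1 is 20 µg with a possible increase to 40 µg in all three places. The extension rule (steps of 10 µg, maxima of 60 µg for Cohort 1 and 80 µg for Cohort 2) is the same in both documents.
- **Outputs that use treatment or dose level.** SAP 8.5 says that treatment, in tables, figures and listings, refers to placebo and the study-drug dose levels. Disposition (SAP 10.0) and the overall adverse-event summary (SAP 17.1.1) are reported by treatment. DXA (SAP 16.2.2.5) is reported by treatment dose level.
- **SAP 14.0.** "Relative Dose Intensity (ratio) = total actual dose received / total planned dose". This is required by cohort, separately for the main period and the extension. The denominator is not defined further.

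**The concern.** Section 8.2.2 is the SAP's analysis grouping, so a programmer would look there for the dose label. The protocol says the C2 doses have been chosen, while the SAP table still shows other values. SAP 7.1, which lists changes from the protocol, is silent on C2 doses. A reader of a table labelled from 8.2.2 would place C2 above C1. A reader of the protocol would place it below.

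The RDI question is separate. The denominator could be the 8.2.2 table, the protocol's cohort dose, the starting dose, or the dose prescribed on each day. The choice decides whether a patient who took every assigned injection appears under-dosed, fully dosed or over-dosed.

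**Working it through.** Neither document states a planned total or an expected RDI, so there is no figure of the plan's own to reproduce. The arithmetic below uses the doses quoted above and 28 daily doses in the Main Treatment Period.

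**1. Labels**

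| | C1 | C2, SAP 8.2.2 | C2, protocol | C2 SAP / protocol |
|---|---|---|---|---|
| Starting dose (µg) | 20 | 40 | 10 | 40/10 = 4.0 |
| Increased dose (µg) | 40 | 60 | 20 | 60/20 = 3.0 |

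At the starting dose, C2/C1 is 40/20 = 2.0 under SAP 8.2.2 and 10/20 = 0.5 under the protocol. The dose order of the cohorts reverses.

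**2. Planned totals over 28 days**

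Both documents allow the increase from Day 14, which gives 13 days at the first dose and 15 at the second. SAP 14.0 flags the increase at Day 15. A first increased dose on that day gives 14 + 14.

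| | No increase | Increase Day 14 | Increase Day 15 |
|---|---|---|---|
| C2, SAP 8.2.2 | 40×28 = 1120 | 40×13 + 60×15 = 1420 | 40×14 + 60×14 = 1400 |
| C2, protocol | 10×28 = 280 | 10×13 + 20×15 = 430 | 10×14 + 20×14 = 420 |
| C1, both documents | 20×28 = 560 | 20×13 + 40×15 = 860 | 20×14 + 40×14 = 840 |

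**3. RDI = actual total / planned total**

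The C2 patient is assumed to be dosed exactly as the protocol text states. This serves only to show how the ratio depends on the denominator.

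- Denominator from 8.2.2, same increase pattern: 280/1120 = 0.25 with no increase, 430/1420 = 0.30 (Day 14), 420/1400 = 0.30 (Day 15).
- Denominator from 8.2.2, starting dose only, patient increased on Day 14: 430/1120 = 0.38.
- Denominator from the protocol, starting dose only, patient doubled on Day 14: C2 430/280 = 1.54. In C1, where the documents agree on dose, 860/560 = 1.54. With the Day 15 convention both are 1.50 (420/280 and 840/560).
- Denominator equal to the dose assigned on each day: 1.00 in every case above.

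The C1 result shows that the undefined denominator is a problem even without the C2 conflict.

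**4. Extension**

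Dosing runs for 56 days from Day 29. Individual titration may start on Day 30, and the dose may go up or down at any time. The documents give a step size and maxima but no planned sequence, so there is no fixed total to divide by.

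**The case against.** The strongest reply is that the SAP treats the C2 dose as open. The 8.2.2 footnote says levels may change, SAP 6.0 gives ceilings that 10 and 20 µg satisfy, and SAP 7.2 provides an interim C1 report to inform the step to C2. On that view no competent programmer would print 40/60 µg against the footnote. This stands in part: mislabelling is conditional on literal use of 8.2.2. But the footnote permits a change without making one, and 8.2.2 drops the ceiling wording used in 6.0.

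Several stronger readings are tempting, and the documents do not support them:

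- **That C2 labels and RDI will be wrong 3- to 4-fold.** SAP 14.0 never refers to 8.2.2, so 0.25 and 0.30 follow only if the denominator is taken from there.
- **That C2 safety, PK and PD tables in general would be mislabelled.** Most Part C summaries are specified by cohort. The dose label matters for the few outputs reported by treatment or dose level. Even there, 8.2.2 has a separate Treatment row without a dose; it is SAP 8.5 that equates treatment with dose levels.
- **That patients would be misgrouped or exposure data corrupted.** Cohort membership, total actual dose, dose intensity and the dose-increase flags rest on allocation, actual doses and dates, and do not change.
- **That the SAP ignored its own source protocol.** SAP 3.0 cites global version 5.0, a Netherlands amendment, and version 7.0 for France, Hungary and Spain. The version of the supplied protocol is not visible. SAP 6.0 gives Days 5, 8 and 11 for reducing supplements, while the protocol gives Days 3, 5 and 8 for C2. That fits text not updated, but does not show whether the SAP missed the selected doses or was drafted before they were chosen.

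It is also fair that RDI is a descriptive ratio in a non-randomised, open-label part with no hypothesis testing, and that no stated objective uses it.

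**Conclusion.** Two defects hold, both with high confidence. First, the C2 dose levels in SAP 8.2.2, SAP 6.0 and the protocol cannot all be the working definition. Second, the RDI denominator is undefined in the main period, and no fixed planned total exists for it in the extension.

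The consequences are conditional, and confidence in them is moderate. Labels would differ from the protocol by 4.0-fold at the starting dose and 3.0-fold at the increased dose, with the C1/C2 order reversed, if 8.2.2 were programmed as written. For a patient dosed as the protocol or agreed C1 text states, RDI would lie anywhere from 0.25 to about 1.54 depending on which of the denominators above is adopted. The 1.54 assumes doubling on Day 14; doubling on Day 15 gives 1.50.

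This should be corrected before database lock. It does not threaten the primary safety assessment, and no position is taken on which C2 dose is right.

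**What to change.** 1. Reconcile the C2 dose levels across the protocol's Part C treatment list and footnotes, SAP 6.0 and SAP 8.2.2 before database lock, and use the reconciled levels wherever outputs are labelled by treatment or dose level. If any difference from the protocol remains, record it in SAP 7.1.
2. In SAP 14.0, define total planned dose as the sum of the doses assigned or prescribed to that patient on each day of the period, including permitted increases.
3. For the extension, compute RDI against the prescribed daily dose, or drop it and keep total dose, dose intensity and the counts of increases and decreases.

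The cost is SAP wording and table labels, with no new data. This assumes that each patient's prescribed dose by day can be recovered from study records. Where it cannot be for the extension, dropping RDI is the simpler course.
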